#### C. Staff change team perception of integration of new practices - NOMAD survey (online)

All current employees of the participating dialysis center or associated CKD practice will be invited. The number of staff is not currently known, but it likely ranges from about 40-50 personnel per site. Staff members participating in the change team will be strongly encouraged to complete the survey through reminders associated with their activities with the collaborative. There are typically five staff members on a change team. Total respondents anticipated: approximately 10 per center X 15 centers = 150 at baseline, repeated at follow-up.

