### 9.0 Study Details

- 9.1 Provide a step-by-step description of the research procedures, study schedule, and interactions with human subjects:
  - Submit all data collection tools that will be used in the study in the Initial Review Submission Packet.

There are three separate study populations for this study, with procedures and instruments specific to each population.

- 1) The first population is seriously ill patients served by the participating dialysis centers and CKD practices. (Instruments A, E, and F)
- 2) The second population is staff of the dialysis center and associated nephrology practices and associated palliative care programs. (Instrument B)
- 3) The third population is a subset of clinical staff who are actively participating with the change team. (Instrument C)

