# B. Staff perception of organizational competence in delivering supportive kidney care - Kidney Supportive Care Implementation Quotient (KSC-IQ on-line survey)

Summative evaluation - before and after the learning collaborative.

We have designed an on-line survey that assesses staff perception of how well their organization delivers supportive kidney care. Survey questions are tied to the best practices in the evidence-based change package. The survey link will be distributed to all local staff associated with the dialysis center, associated nephrology offices, and palliative care or hospice organizations cooperating with the dialysis center. The survey will be conducted at baseline prior to inception of the collaborative. Survey results will be shared with the participating organizations to use as a needs assessment. The survey will be conducted again after the close of the collaborative.

C. Clinical staff and change team perception of integration of new practices - NOMAD survey (online) Both formative and summative evaluation.

We will administer the NOMAD survey to measure staff perception (all dialysis center clinical staff) about the extent to which Pathways best practices have become part of normal work flow. Based on Normalization Process Theory. All dialysis center clinical staff will be invited to complete the survey after the first and third learning periods. Change team participants will be especially encouraged to complete the survey as part of their participation on the change team.

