#### C. Clinical staff and change team perception of integration of new practices - NOMAD survey (online)

- 1. The dialysis center will have the option of an on-line survey or a paper survey to distribute to staff. We have added the paper survey option because many of the dialysis center staff have no or very limited access to internet at the worksite.
- 2. For the online survey, the dialysis center or nephrology center will send an on-line survey link to all of its clinical staff.
- 3. The on-line survey will start with a page which explains the purpose of the survey and describes risks and benefits of participating in the survey. The survey contains a question asking for electronic consent, as follows:

ELECTRONIC CONSENT: Please select your choice below. Clicking on the "Agree" button below indicates that:

- \* You have read the above information
- \* You voluntarily agree to participate
- \* You are at least 18 years of age

Agree

Disagree (this will end the survey)

- 4. The paper survey will have the same informed consent text as the on-line survey. Presumably, staff who do not consent to participate will not submit the paper survey.
- 5. Members of the change team in particular will be strongly encouraged by the Pathways Project staff to complete the NOMAD survey at designated times through email reminders and reminders on regularly scheduled calls.

Change team selection and consent

- The subjects who are part of the intervention team in each dialysis center or associated CKD practice will be identified by the dialysis or CKD clinic management.
- 2. The identified team members will be approached by the research coordinator who will describe the surveys to be completed as part of the study and the time when each survey will need to be completed. The surveys and their timing are listed on the attached measures spreadsheet. Copies of the surveys are also attached. The surveys are the Kidney Supportive Care Implementation Quotient, the NoMAD implementation tool, and the Institute for Healthcare Improvement single-item measure of the dialysis personnel's sense of the progress of the intervention in his/her dialysis center.
- The dialysis or CKD clinic research coordinator will ask for verbal consent from the subject to participate.

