16.6 Is there a data and safety monitoring plan or board (DSMB) for this study?  O Yes • No	
C Yes    No	
O Yes ⊙ No  Privacy and Confidentiality	
O Yes    No  Privacy and Confidentiality  17.1 Which personal or demographic data will be collected?	
O Yes	
Privacy and Confidentiality  17.1 Which personal or demographic data will be collected?  Check all that apply:  Name SSN Medical Record # (MRN) DOB Age Phone # Home Address Email	
Privacy and Confidentiality  17.1 Which personal or demographic data will be collected?  Check all that apply:  Name SSN Medical Record # (MRN) DOB Age Phone # Home Address Email Date of medical procedures	
Privacy and Confidentiality  17.1 Which personal or demographic data will be collected?  Check all that apply:  Name SSN Medical Record # (MRN) DOB Age Phone # Home Address Email	

☐ Department / ☐ Disease Status ☐ City ☐ State / other ☐ Zip Code ☐ Biological sam	S					
• Will any o		lected in the prevent the medical recorport?	-			
Instrument	A. Patient- reported outcomes (telephone survey)	B. Kidney Supportive Care Implementation Quotient (KSC-IQ) on-line survey with paper option	C. Clinical staff and change team perception of integration of new practices - NOMAD survey on-line survey with paper option	D. Facility level monthly report of utilization statistics	E. Baseline and follow- up patient demographic and utilization data	
Mode of administratio n	Telephone survey	Self- administered on-line survey with paper option	Self- administered on-line survey with paper option	Aggregate data from quality improvement reports	Chart review or EMR report	
Mode of adminis	A. Individual Collecting: gen der, ethnicity, race, age, and education NOTE: Name, phone, email and physical address are obtained only for purposes of contacting patient to enroll them in study and then for mailing incentive gift card and copy of information needed for consent. Name, phone, email, and physical address will not remain linked to survey data.	B. Individual Collecting: employer name	C. Individual No personal or demo data collected	D. Aggregate (by center)	E. Individual Non- identifiable data to be collected Demo include age group, sex, race, Medicaid status (proxy for economic status), ESCO status, primary language, vintage (years in dialysis treatment.	
		ode numbers and direct				
O Yes 🖸 No						
17.3 Protections that	will be implemented to	o maintain the confiden	itiality of data, and s	pecimens:		

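### Change-team members could make up as much as half of NoMAD respondents, and the plan describes no item or weighting that would separate them from other staff

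*Combined protocol and SAP*

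**What the plan says.** All references are to the combined protocol and SAP.

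**Whom NoMAD represents.** There are three answers.
- Section 9.1, opening, for Instrument C: "The third population is a subset of clinical staff who are actively participating with the change team".
- Section 9.1 C gives all dialysis center clinical staff as the group whose perception is measured. The consent table in Section 13.2 also names clinical staff, and adds those of the CKD practice.
- Section 10.1 C: "All current employees of the participating dialysis center or associated CKD practice will be invited".

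**Numbers.** Section 10.1 C puts staff at 40-50 per site, while saying that the figure is not yet known. It expects "approximately 10 per center X 15 centers = 150 at baseline, repeated at follow-up". It also states: "There are typically five staff members on a change team".

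**Encouragement.** In the Section 9.1 procedures for NoMAD, step 5 reads: "Members of the change team in particular will be strongly encouraged by the Pathways Project staff to complete the NOMAD survey". The means are emails and reminders on scheduled calls. Under Section 9.6, encouragement of staff at large is general and not aimed at individuals.

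**What is recorded.** The Section 17.1 table says of Instrument C: "No personal or demo data collected". Section 17.3 lists no code link. Section 14.1 says that surveys are coded to the center and that professional categories will be collapsed, which implies that a category is held. No section mentions a team-membership item.

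**Analysis.** Section 8.4 describes no weighting, stratification or non-response adjustment for the staff surveys.

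**The concern.** NoMAD asks whether the new practices have become part of normal work. The change team is the group chosen by management to bring those practices in. A small sample in which that group is over-represented may say more about the implementers than about the staff who were meant to absorb the change.

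Two results are exposed. The first is the level of normalization reported for all clinical staff. The second is the comparison between waves: answering is voluntary (Section 10.8) and members may leave the team at any time (Section 12.3), so the team's share of respondents can differ from one wave to the next. If membership is not captured on an anonymous form, it cannot be recovered afterwards.

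**Working it through.** **1. The plan's own figure.** 10 per center × 15 centers = 150 per round, as stated. It also fits the study-wide maximum of 2520 in Section 10.4: 720 patients + 2 × 750 KSC-IQ + 2 × 150 NoMAD = 2520. So 10 per center is the working planning number.

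**2. Inputs.** Team size 5, respondents 10 and staff S = 40-50 come from Section 10.1 C. The team's response rate r is not stated; I assume 40%-100%. D, the mean score of team members minus that of other staff, is unknown in both size and sign.

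**3. Formulas.**
- Team share of respondents = 5r/10.
- Team share of staff = 5/S, which is 12.5%, 11.1% and 10.0% for S = 40, 45 and 50.
- Shift of an unweighted mean = (5r/10 − 5/S) × D.

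**4. Results.**

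| r (assumed) | Team share of respondents | Shift, S = 40 | Shift, S = 45 | Shift, S = 50 |
|---|---|---|---|---|
| 40% | 20% | 0.075 D | 0.089 D | 0.100 D |
| 60% | 30% | 0.175 D | 0.189 D | 0.200 D |
| 80% | 40% | 0.275 D | 0.289 D | 0.300 D |
| 100% | 50% | 0.375 D | 0.389 D | 0.400 D |

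**5. When the team is over-represented.** This happens whenever r exceeds the overall response rate, 10/S. That rate is 25% at S = 40, 22% at S = 45 and 20% at S = 50.

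**6. Clinical staff as the denominator.** Their number is not given. Assume 20-35, with all 10 respondents clinical. The team is then 5/20 = 25% to 5/35 = 14% of the target group. At r = 100% the shift is (0.50 − 0.25) D = 0.25 D to (0.50 − 0.143) D = 0.36 D. With only 20 clinical staff the overall response is 10/20 = 50%, so the team is over-represented only if r is above 50%. At r = 40% it would be slightly under-represented (20% against 25%).

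**7. Between waves.** With the same D in both waves, the spurious change is (share in wave 2 − share in wave 1) × D. As an illustration only, a move from 30% to 50% (r from 60% to 100%) gives 0.20 D. A stable share and a stable D give no spurious change.

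**The case against.** Several stronger readings are tempting, and the documents do not support them.

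- *Half of the respondents will be team members.* That is the ceiling. It needs every member to answer and the total to stay at 10. No team response rate is given.
- *The team is 11% of the target group.* 5/45 is a share of all employees. As a share of clinical staff it is larger and the gap is smaller.
- *The result will be overstated.* Nothing states that team members score higher, and people close to the change may see its failures more clearly. Upward bias is the likelier direction, since management picked them to carry out the change, but this is a judgment.
- *Membership is not recorded.* The questionnaire is an attachment that is not shown. Section 17.1 is not a full item list either, since Section 14.1 implies a professional category. What can be said is that no membership item is described.
- *The bias cannot be corrected.* It cannot be adjusted by membership with the data described, but it can be bounded by sensitivity analysis.

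Two further objections carry weight. If Instrument C is meant for the change team, as the opening of Section 9.1 says, a high team share is not bias at all. And the stakes are moderate: NoMAD is partly formative, Section 8.4 names no test for it, and the before-and-after survey of all staff is the KSC-IQ, with up to 750 respondents per round.

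What remains is that Section 9.1 C claims all clinical staff, the expected response is low, reminders are targeted at one group, and no means of separating that group is described. None of this depends on full team response.

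**Conclusion.** The concern holds as a risk of bias, conditional on all clinical staff being the target. Team members could be up to half of respondents (20%-50% at an assumed team response of 40%-100%), against 10%-12.5% of all employees or an assumed 14%-25% of clinical staff. With 45 staff, the unweighted mean would shift by about 0.09-0.39 times D, probably upward. The range rests on the plan's 10 respondents and five team members per center; r, the clinical-staff count and D are not in the documents. A change of mix between waves would pass unseen. Separately, the three statements of the Instrument C population conflict, and that conflict depends on no assumption.

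**What to change.** 1. Reconcile the Instrument C population across the opening of Section 9.1, Section 9.1 C and Section 10.1 C. Reconcile the timing as well: Section 9.1 C places the two rounds after the first and third learning periods, while Section 10.1 C speaks of baseline and follow-up.
2. If the target is all clinical staff, confirm that the questionnaire has no membership item. Then add one anonymous yes/no question on change-team membership to the online and paper forms, and collect from each site its counts of team members and clinical staff.
3. Report team and non-team results separately at each wave, with the number of respondents in each group. Do not rest the all-staff normalization conclusion on the unweighted pooled mean.
4. Show a mean weighted to the site's staff mix as a sensitivity analysis, and state its limit. With 45 staff and full team response, 40/45 = 89% of the weight falls on about five non-team respondents per site, who are 5/40 = 12.5% of non-team staff. Their self-selection is not removed.

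The cost is one survey item, two counts per site and a small loss of anonymity. About five people per site would share the yes answer, so the flag alone is consistent with the two-respondent principle in Section 14.1. Crossed with professional category it could identify individuals, so do not cross the two where a cell could hold fewer than two people.

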#### D. Facility-level monthly report of utilization statistics

One report per dialysis center or associated CKD practice will be obtained monthly. These reports cover all patients at the site, but data is only reported in aggregate.

#### E. Patient level demographic and utilization information

This is collected on all patients who are identified as seriously ill, using a validated screening process. At most centers, we expect about 20% of centers at the patient will be identified as seriously ill. We expect 300 patients to be identified at baseline (20% of the 1500 total patients) and another cohort of 300 patients to be identified at follow-up.

#### F. Pathways MMWD CKD Intervention Tracker

This is collected on all patients in CKD site who are identified as seriously ill, have chosen medical management without dialysis (MMWD), or are considering MMWD. This group is part of the 300 patients to be identified at baseline (20% of the 1500 total patients) and another cohort of 300 patients to be identified at follow-up.

#### 10.4 Maximum number of subjects to be enrolled:

- For a multi-center study, both local and total accrual numbers must be provided if GW is acting as the IRB of Record.
- If this study does not involve multiple sites or the number of subjects at other sites is unknown, complete only the "Locally" row.
- Subjects are considered to be enrolled and count towards your total number of subjects once they
  begin study procedures, which excludes screening procedures. A list of subjects who sign the
  informed consent document but did not meet inclusion criteria should be kept for your files.

#### Maximum Number of Subjects to be Enrolled

	Annually	Entire Study
Locally (by GW researchers)		
Study-wide (Multi-center)	1260	2520

#### 10.5 Age range of subjects:

18 years old and older

#### 10.6 Inclusion Criteria:

Order Number	Criteria
1	Patients at least 18 years old who are currently being treated by participating dialysis center.
2	Dialysis patients identified as "seriously ill" by screening with "surprise question"- a validated tool that identifies patients with elevated mortality risk. The treating nephrologist or nurse practitioner or dialysis nurse answers whether they would be surprised if the patient died in the next 6 months.
3	For staff surveys only: Dialysis personnel working in the participating dialysis centers or associated nephrology practice or associated palliative care practice.

#### 10.7 Exclusion Criteria\*:

These are the characteristics that a participant must NOT have in order to be eligible to participate in the study.

Order Number	Criteria
1	Patients with impaired congitive decision making processes as determined by a screening tool.

# \*If excluding a population or group that may benefit from the research, please provide justification:

All patients will potentially receive the impact of changes in care processes implemented by the dialysis and CKD centers. However, only patients who are cognitively able and English or Spanish speaking will be surveyed by phone. We do not have the budget to translate the survey instruments nor hire survey administrators fluent in languages other than English and Spanish.

10.8 Special populations to be involved in the research:	

 
✓ Employees
 
Students
 
Educationally Disadvantaged
 
Economically Disadvantaged
 
Mentally Ill
 
Decisionally-Impaired
 
Illiterate
 
✓ Non-English speaking
 
Research conducted internationally
 
Other
 
	
For any population listed above, please explain why the population is necessary and explain additional steps that will be taken to protect the subjects:	
Dialysis center and/or CKD practice patients: patients are the only ones who can report on whether communication is effective from their point of view. Therefore a direct survey of patients is the only way to obtain patient assessment of whether communication practices have improved as a result of the project. When the survey is explained to them, they will be assured that their care will not change regardless of whether they participate in the survey or not. Also, when the survey administrator introduces the survey, the administrator will remind them that they can skip any questions or stop the survey at any time.	
Non-English speaking: Spanish-speaking patients are a significant proportion of the patients served by the participating dialysis and CKD clinics. At some sites, they are a third or more of patients served. Excluding Spanish-speaking patients would make it more difficult to generalize to this population, and possibly limit their access to the care improvements developed by this project. To protect these patients we are hiring an interviewer who is fluent in Spanish to conduct the consent process and patient interview. The Spanish translation of the survey will be prepared by a professional translator for the portions that are not already available as Spanish translations of validated scales. We will also have an arrangement with a telephone interpreter service available to use if any participating patient has concerns and wants to talk with members of the research team.	
Change team selection criteria and withdrawal mechanism: Change team members are selected by their management to participate in the project. All project participants will receive study information and a consent form. Consent will be given verbally. The participation agreement will state that answering the staff surveys is voluntary and not required. If a staff person wishes to withdraw from the entire project (from participation on the change team), the staff member will be directed to talk with their manager.	
Spanish translation services by a certified and reputable company will be used to translate study documents. These documents include the patient flyer and letter, as well as the telephone questionnaire. A Spanish speaking interviewer will be used to interview these patients. The company used for translation of the documents, as well as the questionnaire is Language Scientific. Their process is outlined in their quote for services, which is included in additional documention portion of this application.	
10.9 Does the research involve prisoners?	
☐ Prisoners	
10.10 Does the research involve children?	
☐ Children	
10.11 Does the research target pregnant women, fetuses or Neonates?	
Pregnant women, fetuses or neonates	
10.12 Does the study involve wards of the state or any other agency, institution, or entity?	
C Yes ⊙ No	

11.0 International/Non-English Speakers	
11.1 If Non-English speakers will be targeted for enrollment, will the consent be translated into the local language(s)?	

 
N/A (participants will all speak English)
 
Yes
 
No
 
In the Initial Review Submission Packet, please submit translated document(s) in the non-English language. For greater than minimal risk studies, please also submit a back translation and a certification of verification of translation by someone who if fluent in the language and include their credentials.
 
	
11.2 International Research:	
Please thoroughly describe the local laws and regulations the IRB should consider in its review of the study being conducted at a foreign site, as applicable:  Not international research.  Is this study also being reviewed by a local ethics committee familiar with the laws/ethical	
codes that might apply to the country?	

✓ N/A (all research taking place is U.S.)

☐ No

☐ Yes

	
The IRB may request the name, contact information, and credentials of someone that is unaffiliated with your research but is familiar with the laws/ethical codes in the country so that the IRB can consult with them if there are questions or concerns about the risks to participants.	
If you have already identified this person, please provide their information:	
